1.5. Benefit-Risk Assessment

This is a FIH study for BGB-DXP604 and the side effects of BGB-DXP604 in humans are unknown.

The healthy subjects in this study will not receive any health benefit from participating in the study other than an assessment of their medical status.

The subjects might have some discomfort from blood collection and other study procedures. Other than that, the risks of study participation include possible adverse reactions associated with BGB-DXP604, such as infusion-related reactions. However, because BGB-DXP604 is a human protein selected from recovered COVID-19 patients, it is unlikely to have any pharmacodynamic effect in healthy subjects. Therefore, the risks are generally low under the current safety monitoring planned for this study.

As exogenous proteins, BGB-DXP604 used alone or in combination with BGB-DXP593 might lead to hypersensitivity reactions, although immunogenicity is considered low due to its human origin. Potential antibody dependent enhancement (ADE) has been observed in some viral infections, such as dengue fever. The possibility of ADE with passive immunity cannot be excluded in COVID-19. However, clinical experiences with respiratory syncytial virus, influenza, and dengue provide strong evidence that the circumstances thought to lead to ADE of disease—including low affinity or cross-reactive antibodies with limited or no neutralizing activity or suboptimal titres—are very rarely implicated as the cause of severe viral infection in the human host (Arvin et al 2020). BGB-DXP604 and BGB-DXP593 are highly potent neutralizing antibodies, and thus are unlikely to cause ADE. In addition, a large number of COVID-19 patients have received convalescent plasma therapy, where no hints of ADE have been identified (Joyner et al 2020).

To further minimize the risk to the subjects, the method of sentinel dosing will be adopted for this study and each healthy subject in the study will receive only a single dose of study drug(s).

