5.2. Dosage, Administration, and Compliance

Planned dose level(s) for study drug(s) in each cohort are presented in [Table 4](#).

Table 4: Planned Dose Level(s) for Study Drug(s) in Each Cohort

Part 1: BGB-DXP604 Alone	Part 2: BGB-DXP604 + BGB-DXP593
Cohort 1A: 10 mg/kg BGB-DXP604 or placebo	Not applicable
Cohort 1B: 30 mg/kg ^a BGB-DXP604 or placebo	Cohort 2A: 30 mg/kg ^b BGB-DXP604 + 30 mg/kg ^b BGB-DXP593 or placebo

Abbreviation: SMC, Safety Monitoring Committee.

^a The dose level of BGB-DXP604 in Cohort 1B may be adjusted based on SMC recommendation.

^b The doses of BGB-DXP604 and BGB-DXP593 in Cohort 2A will be recommended by SMC and not exceed 30 mg/kg for each study drug.

Eligible subjects will receive the administration of study drug(s) at dose level(s) as above or matching placebo for 30 to 60 minutes.

For Cohort 2A, BGB-DXP593 infusion should be administered intravenously first, followed by the intravenous infusion of BGB-DXP604. BGB-DXP604 infusion should be given ≥ 30 minutes after the completion of the BGB-DXP593 infusion. The matching placebo for Cohort 1A and Cohort 1B is normal saline at a volume equal to BGB-DXP604 only; for Cohort 2A, normal saline solutions at a volume equal to BGB-DXP604 or BGB-DXP593 are needed and will be administered at the same sequence as BGB-DXP604 or BGB-DXP593. The dose of study drug(s) will be based on the subject's actual body weight 1 day before the administration of study drug(s) (Day -1).

As a routine precaution, subjects must be monitored for ≥ 2 hours after the infusion of study drug(s) in an area with resuscitation equipment and emergency agents. The study drug(s) must not be administered concurrently with any other drug.

For safety reasons, the first 2 subjects randomized and dosed in each cohort will be monitored for ≥ 48 hours before the remaining subjects receive the same dose of study drug(s).

In this study, after the last subject in the current cohort has received the study drug and has been followed up for ≥ 5 days, the SMC will review the available safety and laboratory data. The next cohort will be initiated after the SMC review.

Accurate records of the study drug(s) received, dispensed, returned, and disposed of should be maintained in the site's Drug Inventory Log. Please refer to the Pharmacy Manual for details regarding study drug(s) management, drug preparation, storage, and administration.

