7.6.2. End-of-Study Visit

Subjects who permanently discontinue from the study will be asked to return to the study center for the End-of-Study (EOS) Visit, which is required to be conducted ≤ 7 days after premature study discontinuation. The Day 113 Visit is the EOS Visit for subjects who complete all previously planned study visits.

If a subject refuses to return for the EOS Visit or is unable to do so, every effort should be made to contact the subject by telephone to determine their health status.

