7.6.3. Safety Follow-up Visit for Premature Study Discontinuation

If a subject discontinues the study ≤ 30 days after the administration of study drug(s), a Safety Follow-up Visit will be conducted 30 days after study drug(s) administration. If premature discontinuation from study occurs ≤ 7 days before 30 days after the administration of study drug(s), the Safety Follow-up Visit may be combined with the EOS Visit if appropriate. A visit window of ± 3 days will be allowed for the Safety Follow-up Visit.

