7.7. Premature Discontinuation From Study Treatment or From the Study

7.7.1. Subject Premature Discontinuation From the Study Treatment

Eligible subjects will receive the administration of study drug(s) and they have the right to discontinue the study drug(s) at any time for any reason during the study treatment. In addition, the investigator has the right to discontinue a subject from the study drug(s) at any time during the study treatment. Subjects who discontinue the study treatment should follow the procedures and the assessments specified in EOS Visit (Section 7.6.2). Subjects who could not complete the infusion or did not receive any study drug after the randomization should be replaced.

The primary reason for discontinuation from the study treatment should be documented on the appropriate eCRF. Subjects may discontinue from the study treatment for reasons that include, but are not limited to, the following:

- Withdrawal of consent
- The investigator or sponsor determines it is in the best interest of the subject
- Significant or persistent AE(s) as described in Section 9.8.

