9.8.2. Severe Hypersensitivity Reactions

If hypersensitivity reaction occurs, the subject must be treated according to the best available medical practice as described in the complete guideline for emergency treatment of anaphylactic reactions according to the ANZCOR Guideline-First Aid Management of Anaphylaxis ([Australian Resuscitation Council 2016](#)). Subjects should be instructed to report any delayed reactions to the investigator immediately.

In the event of a systemic anaphylactic/anaphylactoid reaction, the infusion must be stopped immediately and the subject discontinued from the study. Systemic anaphylactic/anaphylactoid reactions typically manifest within minutes following administration of the drug/antigen and are characterized by respiratory distress; laryngeal edema; and/or intense bronchospasm; and are often followed by vascular collapse or shock without antecedent respiratory difficulty; cutaneous manifestations such as pruritus and urticaria with/without edema; and gastrointestinal manifestations such as nausea, vomiting, crampy abdominal pain, and diarrhea.

The subject will be administered epinephrine injection and dexamethasone infusion if hypersensitivity reaction is observed. The subject should then be placed on monitor immediately and an Intensive Care Unit should be alerted for possible transfer if needed.

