Abbreviations: ADA, antidrug antibody; AEs, adverse events; COVID-19, Coronavirus Disease 2019; D, day; ECG, electrocardiogram; EOS, End-of-Study; HIV, human immunodeficiency virus; Ig, immunoglobulin; IRT, Interactive Response Technology; PK, pharmacokinetic; rRT-PCR, real-time reverse transcription-polymerase chain reaction; SAEs, serious adverse events; SARS-CoV-2, severe acute respiratory syndrome coronavirus 2.

- ^a The schedule of assessments for Day 1 under different timepoints are provided in [Appendix 2](#).
- ^b The EOS Visit will be conducted within 7 days after a premature study discontinuation. The Day 113 Visit is the EOS Visit for subjects who complete all previously planned study visits.
- ^c The Safety Follow-up Visit is only for subjects who discontinue the study within 30 days after the dose of study drug. The Safety Follow-up Visit will be conducted on 30 days after the dose of the study drug (± 3 days). If the premature discontinuation from study occurs within 7 days before the timepoint of 30 days after the dose of the study drug, the Safety Follow-up Visit could be combined with the EOS Visit as appropriate.
- ^d The informed consent must be obtained before performing any study-specific procedures. Consent must be obtained using the current version of the form approved by the Independent Ethics Committee/Institutional Review Board.
- ^e Follicle-stimulating hormone and estradiol assessments will be performed on female subjects who are < 55 years of age with no spontaneous menses for ≥ 12 months to identify the status of no childbearing potential. Female subjects of no childbearing potential and female subjects of childbearing potential who are willing to use a highly effective method of birth control are eligible to participate.
- ^f Subjects will be randomized into either the active arm or control arm via IRT. Randomization will occur after the admission on Day -1 and before the dose of study drug on Day 1.
- ^g The dose will be based on the subject's actual body weight 1 day before the administration of study drug(s) (Day -1). In Cohort 2A, BGB-DXP593 should be administered first and BGB-DXP604 should be administered ≥ 30 minutes after the completion of BGB-DXP593 infusion.
- ^h Height and weight will be measured at screening, and weight will be measured again on Day -1.

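### Protocol Section 9.8.2 removes a subject with anaphylaxis from the study, not only from study drug, leaving one scheduled post-dose ADA sample instead of five and adding no protection

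*Protocol*

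**What the plan says.** **The rule.** Protocol Section 9.8.2: "In the event of a systemic anaphylactic/anaphylactoid reaction, the infusion must be stopped immediately and the subject discontinued from the study". The same section says that such reactions typically appear within minutes of administration.

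**Related rules on stopping.**
- Section 7.7.1, on stopping *treatment*, includes among its reasons "Significant or persistent AE(s) as described in Section 9.8". The list in Section 7.7.2 of reasons for leaving the *study* names no adverse event, though it is not exhaustive.
- Table 6 in Section 9.8.1 withdraws a subject with a Grade 3 or Grade 4 infusion-related reaction from study drug treatment. It does not mention leaving the study.
- Section 7.7.1 also says: "Subjects who discontinue the study treatment should follow the procedures and the assessments specified in EOS Visit (Section 7.6.2"). It does not say whether these subjects continue to Day 113.

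**Dosing.** Section 1.5 limits each subject to a single dose of study drug(s). In Cohort 2A that dose has two infusions, BGB-DXP593 first. Section 5.2: "BGB-DXP604 infusion should be given ≥ 30 minutes after the completion of the BGB-DXP593 infusion".

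**Visits after leaving the study.** The EOS Visit is one "which is required to be conducted ≤ 7 days after premature study discontinuation" (Section 7.6.2). For those who leave within 30 days of dosing, "a Safety Follow-up Visit will be conducted 30 days after study drug(s) administration" (Section 7.6.3). Appendix 1 confines that visit: "The Safety Follow-up Visit is only for subjects who discontinue the study within 30 days after the dose of study drug". Appendix 3 has PK and ADA samples in the Day 113/EOS column and no column for the Safety Follow-up Visit.

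**The concern.** The protective act after anaphylaxis is to stop exposure. With one dosing occasion, exposure ends when the current infusion is stopped and any pending one is cancelled. Leaving the study then does nothing except remove later scheduled observation.

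Immunogenicity is a secondary objective, and protocol Section 10.5 leaves open an evaluation of its effect on PK and safety if the data allow. A subject who has had a systemic hypersensitivity reaction is one whose ADA course a reader of the report would want to see. Under the analysis rules (protocol Section 10.1.2, SAP Sections 6.1 and 6.7), a baseline result and one post-baseline result make a subject evaluable. One very early negative sample would therefore enter the incidence table on the same footing as a full series.

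The rule also sits oddly beside Table 6. Bronchospasm, urticaria and pruritus appear both among the infusion-reaction symptoms and in the description of anaphylaxis. Similar clinical pictures could thus be handled under either text, and only one of the two requires the subject to leave the study.

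**Working it through.** The documents give no figure of their own for this point. The check is a count from the schedules plus a projection from protocol Table 1.

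**1. Timing, with discontinuation dated Day 1**
- Latest EOS Visit: Day 1 + 7 = Day 8 (168 h).
- Safety Follow-up Visit: 30 days after dosing = Day 31, ± 3 days, so Days 28 to 34.
- Planned end: Day 113, which is 112 days after dosing.

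**2. ADA samples (Appendices 3A and 3B, same schedule)**
- Scheduled after dosing: Days 15, 29, 57, 85 and 113/EOS = 5.
- Regular samples on or before Day 8: none.
- Under Section 9.8.2: the early EOS sample only = 1, at least 15 − 8 = 7 nominal days before the first regular one.
- If discontinuation is dated *d* days later, the EOS limit moves to Day 8 + *d*. It reaches Day 15 only if *d* = 7. If the EOS Visit is refused, no scheduled post-dose sample remains.

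**3. Weight in the ADA summary**
- One subject in a six-subject active arm: 1/6 = 16.7%.
- If a replacement is dosed and also evaluable: 1/7 = 14.3%, because the subject who reacted stays in the ADA Analysis Set.

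**4. Routine AE collection (Section 9.7.1: 30 days after dosing or EOS, whichever is later)**
- Under Section 9.8.2: to Day 31, or 30 days. Full schedule: 112 days.
- Lost: 112 − 30 = 82 days, all beyond the 30-day TEAE window of Section 10.3.2.

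**5. PK, for scale only**
- Post-dose samples: 15 (EOI, 6, 24, 48, 72, 96, 168, 336, 504, 672, 1008, 1344, 1680, 2016, 2688 h). Eight of them fall after 168 h.
- Inputs from Table 1, human projection: CL 0.0090 L/h, Vc 3.79 L, Q 0.031 L/h, Vp 1.92 L. Assumptions: linear two-compartment model, bolus approximation.
- k10 = CL/Vc = 0.002375; k12 = Q/Vc = 0.008179; k21 = Q/Vp = 0.016146 (all per h).
- α and β are the roots of x² − (k10 + k12 + k21)x + k10·k21 = 0: α = 0.02518, β = 0.001523 per h. Half-life = ln 2/β = 455 h = 19.0 days.
- Share of AUCinf observed by time t = [(A/α)(1 − e^(−αt)) + (B/β)(1 − e^(−βt))] / (A/α + B/β), with A = (α − k21)/(α − β) and B = (k21 − β)/(α − β).

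| Sampling to | Share of AUCinf |
|---|---|
| Day 8 (168 h) | 25.3% |
| Day 29 (672 h) | 65.4% |
| Day 113 (2688 h) | 98.4% |

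- Share of AUC0-29 observed by Day 8: 25.3/65.4 = 38.7%.
- Under linear PK these shares do not depend on dose, so they also hold for a partial infusion. Whether such a profile is useful is taken up under the objection.

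**6. Attendance**
- Staying in the study: Days 4, 5, 8, 15, 22, 29, 43, 57, 71, 85, 113 = 11 visits after discharge.
- Under Section 9.8.2: EOS and Safety Follow-up = 2.

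**The case against.** **Changing one phrase in 9.8.2 would achieve little.** This stands. Section 7.7.1 sends subjects who stop only treatment to the same EOS procedures and does not say they stay to Day 113. The amendment to 7.7.1 is therefore essential. Section 7.6.2, by contrast, already applies its 7-day rule only to premature *study* discontinuation and needs no edit.

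**The PK objective does not rest on this subject.** This also stands. A subject who cannot complete the infusion is replaced (Sections 3.1 and 7.7.1) on the same treatment (Section 5.3). A partial dose does not represent the 10 or 30 mg/kg level. In Cohort 2A, a reaction to BGB-DXP593 means that no BGB-DXP604 profile exists to lose. A reader might take the 25% coverage in the working as damage to the PK results; the documents do not support that. Replacement does not, however, recover the ADA course of the subject who reacted.

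**Later ADA cannot explain a reaction within minutes of a first dose.** Correct. Pre-existing ADA might, and the predose sample is kept. What is lost is knowledge of whether this subject goes on to form ADA, and a fair entry in the incidence table.

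**The subject is not abandoned.** A reader might infer that safety follow-up ends on Day 8. It does not. The visit at about Day 31 remains, AEs are followed to resolution or stabilization with supplemental tests as indicated (Section 9.4.4), unscheduled visits are allowed (Section 8.5), and related SAEs are reported later (Section 9.7.1). An extra ADA draw is possible, but none is scheduled.

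**Burden.** A healthy volunteer with no prospect of health benefit may reasonably want to stop after such an event. Withdrawal of consent already provides for that without a mandatory exit.

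**Conclusion.** The point holds and is minor. For a subject with systemic anaphylaxis whose discontinuation is dated Day 1, the plan keeps one scheduled post-dose ADA sample instead of five. It still treats the subject as ADA-evaluable, and it drops 82 of 112 days of routine AE collection. Nothing is gained in protection compared with permanently stopping all study drug. An ADA that appears after about Day 8 would go unrecorded unless someone ordered an unscheduled sample, and the subject would be reported as negative, although individual results are listed.

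It would be tempting to say that the primary endpoint is compromised. It is not: TEAEs are counted to 30 days and collection runs to 30 days. Nor do the documents give an event rate. No such reaction may occur among the 18 planned active subjects, in which case the rule has no effect.

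The conclusion assumes that the subject attends the early EOS Visit, that discontinuation is dated close to dosing, and that the subject would have been willing to remain.

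**What to change.** 1. **Section 9.8.2, second paragraph.** Keep the instruction to stop the infusion. Replace the requirement to leave the study with: *all study drug(s) permanently discontinued, including any infusion not yet started; unless consent is withdrawn, the subject remains in the study for the scheduled safety, PK and ADA visits through Day 113.*
2. **Section 7.7.1.** State that every subject who stops treatment after receiving any study drug continues scheduled follow-up to Day 113, in place of an early EOS Visit. Without this, the first change may recover nothing.
3. **Leave unchanged.** Section 7.6.2 and the emergency treatment text in Section 9.8.2.

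The cost is a wording amendment to two sections, with no added subjects and no new procedures. The burden falls on the affected subject, who is asked to attend up to 11 already scheduled post-discharge visits rather than two and may still withdraw at any time.

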10. STATISTICAL METHODS AND SAMPLE SIZE DETERMINATION

Details of the statistical analyses will be included in a separate Statistical Analysis Plan.

10.1. Statistical Analysis

10.1.1. Randomization Method

As discussed in Section 7.4, subjects will be randomized using the IRT system for this study.

10.1.2. Analysis Sets

The Safety Analysis Set will include all subjects who received either study drug.

The PK Analysis Set will include all subjects who received either study drug and had any measurable concentration of study drug(s).

The ADA Analysis Set will include all subjects who received either study drug and for whom both baseline ADA and ≥ 1 postbaseline ADA results are available.

10.1.3. Subject Disposition

The number of subjects randomized, treated, and discontinued from study drug(s) and/or study will be counted. The primary reason for study drug(s) and/or study discontinuation will be summarized according to the categories in the eCRF.

Important protocol deviations will be summarized and listed by each category.

10.1.4. Demographics and Other Baseline Characteristics

Demographic and other baseline characteristics will be summarized in the Safety Analysis Set using descriptive statistics. Summary statistics will be presented for continuous demographic and baseline characteristic variables by treatment group. The number (percentage) of subjects in each category will be presented for categorical variables by treatment group. Continuous variables include, but are not limited to, age, weight, height, and BMI. Categorical variables include, but are not limited to, sex, race, and ethnicity.

10.1.5. Prior and Concomitant Therapy

Concomitant medications will be coded using the World Health Organization Drug Dictionary drug codes and will be further coded to the appropriate Anatomical Therapeutic Chemical code indicating therapeutic classification. Prior and concomitant medications will be summarized by treatment group.

Prior medications will be defined as medications that started before the administration of study drug(s). Concomitant medications will be defined as medications that (1) started before the administration of study drug(s) and were continuing at the time of the administration of study drug(s), or (2) started on or after the date of the administration of study drug(s) ≤ 30 days after the administration of study drug(s).

10.2. Efficacy Analyses

There is no efficacy analysis planned for this study.

10.3. Safety Analyses

AEs, ECGs, vital signs, and laboratory data will be reviewed and summarized on an ongoing basis during the study to evaluate the safety of subjects. Descriptive statistics will be used to analyze all safety data.

10.3.1. Extent of Exposure

The extent of each study drug exposure will be summarized descriptively for the study drug(s) administered by treatment group. The number (percentage) of subjects with dose interruption and infusion rate decreased will be summarized with the respective reasons by treatment group.

Subject data listings will be provided for all dosing records and for calculated summary statistics.

10.3.2. Adverse Events

The AE verbatim descriptions (as recorded by the investigator on the eCRF) will be classified into standardized medical terminology using the Medical Dictionary for Regulatory Activities (MedDRA). AEs will be coded to MedDRA by the lowest level term, preferred term (PT), and primary system organ class (SOC).

A TEAE is defined as an AE that had an onset date or a worsening in severity from baseline on or after the administration of study drug(s) and ≤ 30 days after the administration of study drug(s). Only those AEs that were treatment emergent will be included in summary tables.

The incidence of TEAEs will be reported as the number (percentage) of subjects with TEAEs by SOC and PT. A subject will be counted only once by the highest severity grade according to NCI-CTCAE v5.0 within a SOC and PT, even if the subject experienced ≥ 1 TEAE within a specific SOC and PT. The number (percentage) of subjects with TEAEs will also be summarized by relationship to the study drug(s).

Treatment-related AEs include those events considered by the investigator to be related to study drug(s) or with missing assessment of the causal relationship. Treatment-emergent SAEs and treatment-related TEAEs will be summarized. All AEs, treatment-emergent or otherwise, will be presented in subject data listings.

